4. TREATMENTS

4.1 TREATMENTS TO BE ADMINISTERED

4.1.1 Identity of BI investigational product and comparator products

The investigational product dabigatran etexilate and the comparator warfarin will be supplied by Boehringer Ingelheim Pharma GmbH & Co. KG, Germany. The composition of these drugs capsules are detailed in Table 4.1.1: 1 and [Table 4.1.1:2](#).

Table 4.1.1: 1 Dabigatran etexilate (Investigational drug)

Substance:	Dabigatran etexilate
Brand name:	Pradaxa®
Pharmaceutical formulation:	Capsule
Source:	Boehringer Ingelheim Pharma GmbH & Co. KG, Germany
Unit strength:	110mg and 150mg
Total Daily dose	220mg; 300mg 1 x 110mg capsule b.i.d. (total daily dose 220mg) 1 x 150mg capsule b.i.d. (total daily dose 300mg)
Route of administration:	p.o.

The main excipients of the dabigatran capsule include tartaric acid, acacia, hypromellose, dimeticone, talc, hydroxypropylcellulose, HPMC (hydroxypropylmethylcellulose) capsule shell, consisting of titanium dioxide (E171), FD & C yellow 6/Sunset Yellow (E110), FD & C Blue 2/Indigo Carmine (E132), hypromellose carrageenan and potassium chloride.

Proprietary confidential information.

© 2016 Boehringer Ingelheim International GmbH or one or more of its affiliated companies. All rights reserved.

This document may not - in full or in part - be passed on, reproduced, published or otherwise used without prior written permission.

Table 4.1.1: 2 Warfarin (active comparator)

Substance:	Warfarin
Pharmaceutical formulation:	Tablet
Source:	Teva UK Limited, UK
Total Daily dose	1mg; 3mg; 5mg As needed to maintain a target INR of 2.0- 3.0 (2.0-2.5 if feasible)
Route of administration:	p.o.

For easy identification warfarin tablet strengths will have a different colour label.

The warfarin sodium tablets are composed of lactose monohydrate, starch (pregelatinised, maize), dispersed erythrosine lake, sodium starch glycolate and magnesium stearate.

Patients will take the warfarin q.d.. The individual doses will be titrated without splitting of the tablet as needed to maintain a target INR of 2.0 - 3.0. If feasible, an INR of between 2.0 – 2.5 should be targeted. INR will be measured at least every two weeks for the first three months in patients newly commencing warfarin, otherwise at least every month throughout the study (more frequently immediately after initiation of warfarin therapy or if required, according to clinical judgement).

All patients will also take clopidogrel (75mg q.d.) or ticagrelor (90mg b.i.d.) according to the local label for at least 12 months after randomisation (in addition to either dabigatran etexilate or warfarin). After 12 months of treatment the clopidogrel or ticagrelor can be discontinued or switched to ASA (≤ 100 mg q.d.) at the discretion of the Investigator.

For patients randomised to receive warfarin:

Patients randomised to receive warfarin will receive ASA (≤ 100 mg q.d.) for either one month in patients with a BMS and for three months in patients with a DES.

Warfarin and dabigatran etexilate supplies will be managed using the IRT system.

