4.2.2 Restrictions

4.2.2.1 Restrictions regarding concomitant treatment

Corticosteroids or NSAIDs may be used if clinically indicated according to current treatment guidelines but it is strongly recommended to avoid these if possible. It should be noted that the use of any of these agents with warfarin or dabigatran etexilate is likely to increase the risk of bleeding.

The following treatments should not be taken during the active treatment phase of the trial:

1. Treatment with ticlopidine or prasugrel
2. Fibrinolytic agents (see [Section 4.2.1.4](#) for exception)
3. GPIIb/IIIa antagonists (e.g. abciximab, tirofiban)
4. Treatment with systemic ketoconazole, itraconazole, posaconazole, cyclosporine, tacrolimus, dronedarone and rifampicin, phenytoin, carbamazepine or St. John's Wort
5. Dipyridamole, rivaroxaban, apixaban and edoxaban, or other oral anticoagulants (e.g. VKAs)
6. ASA - except where specified in the protocol for patients randomised to the warfarin arm or in both treatment arms after 12 months of treatment if clopidogrel or ticagrelor is switched to ASA ($\leq 100\text{mg q.d.}$) at Investigator discretion. The patients should be advised to not use additional ASA-containing over-the-counter medications.

The Investigator is alerted to the use of concomitant administration of moderate to strong P-gp inhibitors (e.g. such as amiodarone, verapamil, quinidine, nelfinavir, posaconazole, ritonavir, saquinavir and tipranavir+ritonavir or lopinavir+ritonavir) or P-gp inducers in this study due to a potential risk of higher or lower plasma levels of dabigatran and consequent exaggerated or reduced pharmacodynamic effect of dabigatran etexilate (notably bleeding risk). Concomitant use of such drugs is not prohibited in this study *per se* (except for treatment with ketoconazole, itraconazole, posaconazole, cyclosporine, tacrolimus, dronedarone, rifampicin, phenytoin, carbamazepine or St. John's Wort), but should be used with caution or, at Investigator discretion, switched to a suitable alternative.

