D2.1	Prohibited medication use	
The following treatments should not be taken during the active treatment period of the trial (at least one on-treatment use, unless otherwise stated):
 
 1. Treatment with ticlopidine or prasugrel 2. Fibrinolytic agents (see Section 4.2.1.4 of the protocol for exceptions) 3. GPIIb/IIIa antagonists (e.g. abciximab, tirofiban) 4. Treatment with systemic ketoconazole, itraconazole, posaconazole, cyclosporine, tacrolimus, dronedarone and rifampicin, phenytoin, carbamazepine or St. John's Wort (only applicable to patients randomised to dabigatran etexilate) 5a. Dipyridamole (although it is allowed for exceptional cases based on CTP Section, 4.2.1.4; for the PPS analyses all patients with on-treatment use will be excluded), 5b. Other oral anticoagulants (e.g. VKAs) 
Commercial NOACs (dabigatran, rivaroxaban, apixaban and edoxaban):
 
Warfarin Patients: At the end of the treatment, flag patients with more than 2 days of overlap of warfarin and commercial NOAC + flag any days of overlap during the treatment period (except for washout of previous treatment/titration at study start (see IPV C4))
 
Dabigatran patients: At the end of treatment, flag patients with more than 1 day of overlap of dabigatran and commercial NOAC + flag any days of overlap during the treatment period (except for washout of previous treatment/titration at study start (see IPV C4))
 
Commercial VKAs:
 
Dabigatran patients: At the end of treatment, flag patients with more than 5 days of overlap of dabigatran and commercial VKA +flag any days of overlap during the treatment period (except for washout of previous treatment/titration at study start (see IPV C4))
 
Warfarin patients: At the end of treatment, flag patients with more than 1 day of overlap of warfarin and commercial VKA. +flag any days of overlap during the treatment period (except for washout of previous treatment/titration at study start (see IPV C4))
 
 6. ASA in the first 12 months for all patients – except for in the first month for warfarin patients with a BMS or the first three months for warfarin patients with a DES (consecutive use of more than 14 days) 	PPS

Table 6.2: 1 (continued) Important protocol violations

Category/ Code	Description	Example/Comment	Excluded from
D2.2	Prohibited use of heparin	Any on-treatment use of heparin where no medical indication is given.	PPS

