D3.1	Mandatory medication not taken per protocol (ASA)	ASA not taken for the first month for warfarin patients with a BMS or for the first three months for patients with a DES as indicated on the Trial Medication Compliance eCRF page (exclude if at least one visit is ticked "No").	PPS, but only from start of non-compliance onwards
D3.2	Mandatory medication not taken per protocol (clopidogrel/ticagrelor)	Clopidogrel/ticagrelor non-compliance during the first 12 months of treatment as indicated on the Trial Medication Compliance eCRF page (exclude if at least one visit is ticked "No").	PPS, but only from start of non-compliance onwards
G	Trial Specific Protocol Violations		
G1	Patient not withdrawn from treatment if CrCl drops to <30mL/min at two different occasions during the trial	As per study protocol, this only applies to patients randomised to dabigatran etexilate.	PPS

KEY: PPS – Per Protocol Set

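### SAP violation D3.1 omits 'warfarin' for drug-eluting stents, so its aspirin rule conflicts with the protocol and with D2.1 and could distort the per-protocol sensitivity analysis (minor)

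*Protocol*

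**What the plan says.** The protocol is consistent. Sections 3.1 and 4.1.1 give aspirin only to the warfarin arm ("Patients randomised to receive warfarin will receive ASA"), for one month with a BMS and three with a DES. Section 4.2.2.1 lists as not to be taken during active treatment "ASA - except where specified in the protocol for patients randomised to the warfarin arm", and otherwise allows it only after 12 months, if clopidogrel or ticagrelor is switched to aspirin.

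SAP Table 6.2: 1 has two rows on aspirin:

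- **D2.1 item 6 (prohibited use)** covers "ASA in the first 12 months for all patients". Its exception names warfarin patients for both stent types, the DES part being "the first three months for warfarin patients with a DES (consecutive use of more than 14 days"). Sustained use outside the exception excludes the patient from the per-protocol set (PPS).
- **D3.1 (mandatory use)** is described as "Mandatory medication not taken per protocol (ASA"). Its comment column reads "ASA not taken for the first month for warfarin patients with a BMS or for the first three months for patients with a DES". The trigger is a single visit ticked 'No' on the Trial Medication Compliance eCRF page. The consequence is exclusion from the PPS from the start of the non-compliance.

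SAP 6.3 makes the full analysis set (FAS) the main set and assigns the PPS to the primary endpoint for sensitivity purposes. SAP 7.4 names the PPS among the checks on the robustness of the primary analysis.

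**The concern.** In D3.1 the word 'warfarin' is attached to the BMS half only. The DES half has no arm limit, so its plain wording reaches DE-DAT patients, for whom the protocol prescribes no early aspirin. Two rows of one table then pull in opposite directions: D3.1 flags a DE-DAT patient with a DES for not taking aspirin, and D2.1 flags the same patient for taking it for more than 14 consecutive days.

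Elsewhere the table states arm limits openly. D2.1 item 4 and G1 are each confined to patients randomised to dabigatran. A programmer could therefore fairly take an unqualified phrase to mean all arms.

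At stake is the per-protocol check on a non-inferiority result. A literal rule would remove adherent follow-up from the two test arms and none from the control arm, and would select by stent type. That is differential exclusion, not only lost precision.

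**Working it through.** The plan states no figure on this point, so the check compares the rules and works through the cases.

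**1. Who should take early aspirin**

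| Source | BMS, month 1 | DES, months 1 to 3 |
|---|---|---|
| Protocol 3.1 and 4.1.1 | warfarin arm | warfarin arm |
| Protocol 4.2.2.1 | barred except in the warfarin arm | barred except in the warfarin arm |
| SAP D2.1 item 6 | exception for warfarin patients | exception for warfarin patients |
| SAP D3.1 | mandatory for warfarin patients | mandatory, no arm named |

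The last cell is the only one out of line.

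**2. A DE-DAT patient with a DES**, supposing that 'No' is ticked whenever aspirin was not taken

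| Aspirin use in the first three months | D2.1 item 6 | D3.1 as written | D3.1 limited to warfarin |
|---|---|---|---|
| None (adherent) | no | **violation** | no |
| Up to 14 consecutive days | no | **violation** | no |
| More than 14 consecutive days, less than three months | violation | **violation** | no |
| Full three months | violation | no | no |

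As written, every row ends in a PPS violation, including the row for exact adherence. With the limit, only use beyond 14 consecutive days is flagged, by D2.1.

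**3. Other patients.** DE-DAT patients with a BMS are never reached by D3.1 under either reading. Warfarin patients are classified the same way under both readings. The conflict is confined to DE-DAT patients with a DES.

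**4. Does the trigger exist?** The compliance page is used in the DE-DAT arms: SAP 7.3 takes dabigatran compliance from it, and D3.2 takes clopidogrel or ticagrelor compliance from it. Whether it also carries an aspirin item for those arms, and whether that item would be ticked 'No' or left blank, is not stated.

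**5. Reach.** Patients affected = 1668 × (DES share) × (fraction with a 'No' tick), where 1668 = 2 × 834 planned DE-DAT patients (protocol 7.6). Neither factor is in the documents. With no such tick the result is 0. With a tick for everyone, an assumed DES share of 50% gives 1668 × 0.50 = 834, and 95% gives 1668 × 0.95 = 1585. These are the ends of a range, not a forecast.

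**The case against.** The strongest reply is that the row already limits itself. Its description speaks of mandatory medication not taken per protocol, and early aspirin is mandatory only in the warfarin arm, so a DE-DAT patient without aspirin has omitted nothing mandatory. The disputed text is in the example/comment column. It follows the shape of protocol 4.1.1, where 'warfarin' is said once for both stent types. D2.1 item 6 makes the intent plain, and SAP 3 assumes that the reader knows the protocol. SAP 6.2 and 6.3 also have the trial team identify most violations and document set membership at the report planning or database lock meeting, so adherent patients would have to be dropped without anyone noticing.

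Most of this stands. It makes a drafting slip far more likely than an intended rule, and it lowers the severity. It does not make the text right. The comment column carries the operative condition and trigger, and SAP 6.2 expects some violations to be identified programmatically after database lock, so the condition should be unambiguous beforehand.

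A reader might go further and infer that the per-protocol comparison would lose a calculable amount of power. The documents do not support that. They set no power for the PPS and give no DES share, and they do not show that an aspirin 'No' can be recorded in the DE-DAT arms.

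**Conclusion.** The inconsistency is real and minor. D3.1's DES half conflicts with protocol 3.1, 4.1.1 and 4.2.2.1 and with D2.1 item 6, most probably through a dropped word.

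Harm needs two conditions together: the rule is coded literally, and aspirin compliance is ticked 'No' for DE-DAT patients. If both held, per-protocol follow-up of adherent DE-DAT patients with a DES would be cut from the first 'No', in the test arms only, and the PPS analysis of the primary endpoint would be distorted. If either fails, there is no effect.

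It would be wrong to infer that the trial's conclusion is at risk. The primary analysis is on the FAS (SAP 7.4), no step of the testing hierarchy specifies the PPS, and SAP 6.3 allows PPS analyses to be omitted when fewer than 10% of the treated set are excluded. It would also be wrong to infer that the sponsor meant to require aspirin in the DE-DAT arms, because every other statement in both documents says the contrary.

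**What to change.** In SAP Table 6.2: 1, row D3.1, insert 'warfarin' before 'patients' in the DES half, so that it matches the corresponding phrase in D2.1 item 6 ("or the first three months for warfarin patients with a DES"). Add a sentence that D3.1 applies only to patients randomised to warfarin-TAT. Check that the program condition for D3.1 includes randomised arm. This aligns the SAP with the sponsor's own protocol and changes no treatment rule. The cost is one word, one sentence and one line of program logic.

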4.1.2 Method of assigning patients to treatment groups

Inclusion and exclusion criteria should be assessed at screening to ensure inclusion of eligible patients. After having signed the informed consent form, patients should complete the screening visit including specified procedures (see the [Flow Chart](#)).

Eligible patients who meet all inclusion and none of the exclusion criteria at Visit 2 will be randomised to receive either dabigatran etexilate 110mg, dabigatran etexilate 150mg or warfarin (see [Section 3.1](#)). In addition, patients will be stratified by age (<80 or ≥ 80 years

Proprietary confidential information.

© 2016 Boehringer Ingelheim International GmbH or one or more of its affiliated companies. All rights reserved.

This document may not - in full or in part - be passed on, reproduced, published or otherwise used without prior written permission.

old) and region (Europe (EU)/Rest of World (ROW) or USA). This stratification will be performed dynamically by the IRT.

The dose of warfarin for the patient will be adjusted to ensure the INR for the patient is maintained at a level of 2.0 – 3.0. If feasible, an INR of between 2.0 – 2.5 should be targeted.

Patient assignment to the treatment groups will be determined by IRT. Access to the randomisation code will be controlled and documented. All necessary instructions for using the IRT will be described in a user guide/manual, a copy of which will be available in the ISF.

The IRT will assign the correct kit number for dabigatran etexilate for the patients at each time point, but for the warfarin patients, individual management will be by the Investigator.

4.1.3 Selection of doses in the trial

The doses of dabigatran etexilate selected for this trial are the same as those used in RE-LY, the Phase III trial for stroke prevention in atrial fibrillation (SPAF). In RE-LY, a dose of dabigatran etexilate 110mg b.i.d. was shown to be comparable to warfarin (INR level 2.0–3.0) for preventing strokes and SE and superior (relative risk reduction of 20%) when considering major bleeding risk [[U09-3249-02](#)]. Moreover, there was an approximate 60% reduction in intracranial haemorrhage with both dosages of dabigatran etexilate.

4.1.4 Drug assignment and administration of doses for each patient

Each patient will be randomised at Visit 2 to receive either dabigatran etexilate (110mg or 150mg b.i.d.) or warfarin. The first dose of trial medication will be taken, between 6 hours after sheath removal and preferably within 72 hours post PCI, with haemostasis assured, however up to 120 hours post PCI is allowed.

Patient randomised to receive dabigatran etexilate:

It is permitted for patients to receive bridging therapy with a parenteral anticoagulant according to local practice before switching to dabigatran etexilate. Dabigatran etexilate should be given 0-2 hours prior to the time that the next dose of parenteral anticoagulant would be due, or at the time of discontinuation in case of continuous treatment (e.g. intravenous (i.v.) unfractionated heparin (UFH)). See [Appendix 10.1](#) for guidance how to switch from an anticoagulant to dabigatran etexilate.

Dabigatran etexilate capsules should be taken in the morning and in the evening (one at each timepoint), at the same time every day with a full glass of water. The capsules must not be crushed, nor opened and can be taken with or without food. If dyspeptic symptoms occur, the Investigator should consider adding a proton pump-inhibitor (PPI) or H2-blocker to the concomitant therapy of the patients.

The interval between doses should be as close to 12 hours as possible.

If a dose of dabigatran etexilate is missed for any reason, the forgotten dose may still be taken up to six hours prior to the next scheduled dose. From six hours prior to the next scheduled

Proprietary confidential information.

© 2016 Boehringer Ingelheim International GmbH or one or more of its affiliated companies. All rights reserved.

This document may not - in full or in part - be passed on, reproduced, published or otherwise used without prior written permission.

dose on, the “missed” dose should be omitted. A double dose to make up for missed individual doses must not be taken.

Any patient that decides to discontinue study medication should be considered for a switch to an appropriate (non-study) anticoagulant according to local practice. For patients receiving dabigatran etexilate, continuation of study drug for 2-3 days to assist bridging may be appropriate. For recommendations on how to switch from dabigatran etexilate to other anticoagulants see [Appendix 10.2](#)).

Patient randomised to receive warfarin:

Anticoagulant bridging therapy (according to local practice) is at the discretion of the Investigator (see [Appendix 10.1](#)).

Warfarin compliance will be monitored by means of the INR rather than by pill counts as it is a more accurate and biologic measure of pharmacodynamic effect than pill counts. Warfarin patients will usually be managed by their Investigator. However, Investigators will also be able to assign INR monitoring to a local anticoagulation clinic. All dose adjustment will be done according to usual clinical practice. The Investigator will be responsible for reporting INR results and the dose of warfarin prescribed.

For patients initiating warfarin, INR should be measured at least every two weeks for the first three months to obtain target INR as soon as possible and to avoid over- or under-dosing. Thereafter, minimum acceptable intervals for INR measurements are every month. More frequent INR measurements will be done as necessary at the discretion of each Investigator or anticoagulation clinic.

To aid Investigators, a validated normogram, will be provided which will indicate recommended dose changes and INR re-testing times for different INR values. This normogram requires more frequent INR monitoring after out-of-range INR values have occurred.

Numerous factors, alone or in combination, may influence the patient’s response to anticoagulants. Thus to ensure adequate control it is recommended that additional INR measures are done when other medications are initiated, discontinued or taken irregularly and/or diet changes. All patients should be educated about potential interactions with other medications, herbal preparations and foods and about the importance of monitoring. INR measurements can be performed independently from the scheduled study visits (see [Flow Chart](#) and [Section 6](#)), however all available INR values should be entered into the eCRF. It is critical to obtain the best possible level of INR control.

Regular study treatment will be completed with the last dose of trial medication being taken on the evening before or the morning of the EOT visit. If the trial medication is to be terminated the patient should switch to an appropriate (non study) anticoagulant according to the local practices.

For recommendations on switch from dabigatran etexilate and study warfarin to other anticoagulants see [Appendix 10.2](#).

Proprietary confidential information.

© 2016 **Boehringer Ingelheim International GmbH or one or more of its affiliated companies. All rights reserved.**

This document may not - in full or in part - be passed on, reproduced, published or otherwise used without prior written permission.

Clopidogrel or ticagrelor

All patients will also receive clopidogrel or ticagrelor for at least 12 months following randomisation. The decision as to whether the patient should receive clopidogrel or ticagrelor is at the discretion of the Investigator. This background medication will not be provided as part of the clinical trial supplies, unless required by local laws and regulations.

ASA:

Patients who require ASA treatment as detailed in [Section 4.1.1](#) will also receive ASA (≤ 100 mg per day). This background medication will not be provided as part of the clinical trial supplies, unless required by local laws and regulations.

